6.5.2 Procedures for handling incorrectly allocated patients

Subjects who fail to meet the eligibility criteria should not, under any circumstances, be enrolled or receive study medication. There can be no exceptions to this rule. Subjects who are enrolled, but subsequently found not to meet all the eligibility criteria must not be assigned into a module or initiated on treatment, and must be withdrawn from the study. Where a subject does not meet all the eligibility criteria but is assigned into a module in error, or incorrectly started on treatment, the Investigator should inform the Medical Monitor immediately, and a discussion should occur between the Medical Monitor and the Investigator regarding whether to continue or discontinue the subject from treatment. All decisions must be appropriately documented.

6.6 Concomitant therapy

The following treatments and the medications listed in [Appendix J](#) are prohibited or are to be used with caution while patients are receiving AZD4635. Details for other study treatments are provided in the modular-specific appendix.

Table 5 Restricted medications

Medication/class of drug:	Usage (including limits for duration permitted and special situations in which it is allowed):
CYP1A2 inhibitors or inducers.	Contribution of CYP1A2 to AZD4635 metabolism appears to be approximately 80%. Potent inhibitors or inducers of CYP1A2 should be avoided during administration of AZD4635. Refer to Appendix J for a list of the prohibited medications.

Table 6 Prohibited medications

Prohibited medication/class of drug:	Additional Information
No other investigational therapy should be given to patients. No anticancer agents other than the study medications should be given to patients.	If such agents are required for a patient, then the patient must first be withdrawn from the study.
Since AZD4635 is an in vitro inhibitor of BCRP (IC ₅₀ 6.2 μM) and OAT1 (IC ₅₀ 6.6 μM), there is a risk of DDIs with sensitive substrates of BCRP (both in the gut and systemically) and OAT1 (systemically). Modelling has predicted a substantial increase in the exposure (>2 fold) of certain statins (simvastatin, rosuvastatin, and atorvastatin) when co-administered with AZD4635. The use of sensitive substrates of OATP1B1/3, OCT1, OCT2, MATE1 and P-gp is also prohibited in this study.	Use of potent inhibitors or inducers of BCRP and sensitive substrates of OATP1B1/3, OAT1, OCT1, OCT2, MATE1 and P-gp is therefore prohibited in the current study (see Appendix J).
Herbal preparations/medications are not allowed throughout the study. These herbal medications include, but are not limited to: St. John’s wort, kava, ephedra (ma huang), ginkgo biloba, dehydroepiandrosterone (DHEA), yohimbe, saw palmetto, and ginseng.	Patients should stop using these herbal medications 7 days prior to first dose of AZD4635. Exceptions may be agreed, but the circumstances must be reviewed by the Medical Monitor in advance.

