7 DISCONTINUATION OF TREATMENT AND PATIENT WITHDRAWAL

7.1 Discontinuation of study treatment

Patients that discontinue 1 study drug may remain on the study and receive other study drug(s) as long as they are continuing to derive clinical benefit (see Section 8.4.6). Patients may be discontinued from study drug(s) in the following situations:

- Patient decision. The patient is at any time free to discontinue treatment, without prejudice to further treatment.
- Any AE that, in the opinion of the Investigator or AstraZeneca, contraindicates further dosing or meets the criteria for discontinuation as defined in the dose modification guidance or prescribing information for the study drug(s).
- Investigator decision or severe non-compliance with the Clinical Study Protocol
- Confirmed disease progression unless, in the opinion of the Investigator, the patient is still receiving clinical benefit. Patients will continue study treatment until objective disease progression, or beyond RECIST 1.1 defined progression if patient is receiving clinical benefit, as judged by the Investigator and in the absence of discontinuation criteria. Tumor assessment must continue while patient continues to receive study treatment as per Section 8.1.1.

- Patients incorrectly initiated on study drug(s) (e.g., patient is determined to have met one or more of the exclusion criteria for study participation at study entry and continuing investigational therapy might constitute a safety risk)
- Patient started alternative anticancer therapy including another investigational agent
- Patient lost to follow-up

Note that discontinuation from study treatment is NOT the same thing as a complete withdrawal from the study.

See the SoA of the assigned module for data to be collected at the time of treatment discontinuation and follow-up and for any further evaluations that need to be completed. The reason for study drug and combinational agent discontinuation will be recorded in the eCRF.

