7.1.1 Procedures for discontinuation of study treatment

The Investigator should instruct the patient to contact the site before or at the time if study treatment is stopped. Discontinuation of study treatment, for any reason, does not impact the patient's participation in the study. A patient that decides to discontinue study treatment will always be asked about the reason(s) and the presence of any AEs. The date of last intake of study treatment and the combinational agent should be documented in the eCRF. All study treatment should be returned by the patient at his next on-site study visit or unscheduled visit. Patients permanently discontinuing study treatment should be given locally available standard of care therapy, at the discretion of the Investigator.

The patient should continue attending subsequent study visits and data collection should continue according to the study protocol. If the patient does not agree to continue in-person study visits, a modified follow-up must be arranged to ensure the collection of endpoints and safety information. This could be a telephone contact with the patient, a contact with a relative or treating physician, and/or information from medical records. The approach taken should be recorded in the medical records. A patient who agrees to modified follow-up is not considered to have withdrawn consent or to have withdrawn from the study.

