7.3 Withdrawal from the study

A patient may withdraw from the study (e.g., withdraw consent) at any time (study drug(s) and assessments) at his own request, without prejudice to further treatment. The reason for patient withdrawal will be recorded in the eCRF.

If a patient decides to withdraw from the study, including study treatment, the investigator needs to confirm whether the patient:

- Withdraws consent to all further participation in the study including any further follow up (e.g., survival contact telephone calls)

OR

- Withdraws consent from study treatment, but agrees to follow-up procedures (as defined in Section 7.1).

A patient who considers withdrawing from the study must be informed by the Investigator about modified follow-up options (e.g., telephone contact, contact with a relative or treating physician, or information from medical records).

If the patient withdraws consent for disclosure of future information, the Sponsor may retain and continue to use any data collected before such a withdrawal of consent.

If a patient withdraws consent to the use of mandatory biological samples, the samples will be disposed of/destroyed if possible and the action documented. If samples have already been analyzed, the sponsor is not required to destroy the results of this research.

A patient who withdraws consent will always be asked about the reason(s) and the presence of any AEs. The Investigator will follow up with patients as medically indicated.

In the event that the patient has actively withdrawn consent to the processing of his personal data, the vital status of the patient can be obtained by site personnel from publicly available resources where it is possible to do so under applicable local laws

See the SoA in the relevant module for data to be collected at the time of study drug discontinuation and follow-up and for any further evaluations that need to be completed. All study drug should be returned by the patient.

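### Table 6 withdraws from the study any patient who needs another anticancer agent, while the discontinuation, follow-up and endpoint sections keep that patient under follow-up (minor internal inconsistency)

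*Protocol*

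**What the plan says.** Section 6.6 governs treatments restricted or barred during AZD4635 dosing. In Table 6, the row on other investigational and anticancer agents gives this instruction: "If such agents are required for a patient, then the patient must first be withdrawn from the study".

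Section 7.1 lists the situations in which study drug may be discontinued. One is "Patient started alternative anticancer therapy including another investigational agent". The section then adds: "Note that discontinuation from study treatment is NOT the same thing as a complete withdrawal from the study".

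Section 7.1.1 says that stopping study treatment, whatever the reason, leaves participation unchanged. It expects further therapy: "Patients permanently discontinuing study treatment should be given locally available standard of care therapy, at the discretion of the Investigator". It also expects observation to go on: "The patient should continue attending subsequent study visits and data collection should continue according to the study protocol".

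Section 8.2.8.2 follows patients who stop before objective progression, with PSA, CT/MRI/PET and bone scans every 3 months. This ends at confirmed progression, withdrawal of consent, the primary data cut-off, or termination of the study or module. Section 8.2.8.3 follows survival and subsequent cancer therapy. In Section 9.4.4, rPFS and OS both count events whether or not the patient has received another anticancer therapy.

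**The concern.** One event, the need for another anticancer agent, has two different exits. Under Table 6 the patient leaves the study. Under Sections 7.1 to 9.4.4 the patient leaves study drug and stays under observation.

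The difference matters for a patient who switches before progression is documented or confirmed. If the site treats him as withdrawn and stops imaging, there are no later scans. His rPFS is then censored at the last evaluable assessment, although the definition asks for follow-up through the new therapy. Duration of response takes its end date, or its censoring date, from progression-free survival, so it is cut at the same place. This is a conduct instruction, so the SAP cannot repair it: no analysis rule recovers scans that were never taken.

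**Working it through.** The check is a comparison of text. The protocol gives no figure on this point to reproduce.

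**Step 1. Set the rules side by side for a patient who starts another anticancer agent.**

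| Place | What happens |
|---|---|
| 6.6, Table 6 | Withdrawn from the study before the agent is given |
| 7.1 | Study drug discontinued; stated not to be complete withdrawal |
| 7.1.1 | Participation unaffected; standard therapy given; visits and data collection continue |
| 8.2.8.2 | Scans and PSA every 3 months; new therapy is not a stopping reason |
| 8.2.8.3 | Survival and subsequent therapy followed |
| 9.4.4, rPFS and OS | Events count regardless of new therapy |

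Table 6 is the only row that takes the patient out of the study.

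**Step 2. Ask whether withdrawal from the study is merely another name for stopping drug.** Section 7.3 describes it as covering both drug and assessments. Section 8.2.8.3 places withdrawn patients beside those lost to follow-up, as people whose status must be sought from notes and registries. Section 6.5.2 uses the term for ineligible patients who must not start treatment. A literal reader therefore has support for taking Table 6 to mean that assessments end.

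**Step 3. Follow the literal reading to the endpoints.** There are two routes.

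- *Switch with no progression yet seen.* The patient is censored at his last scan instead of being scanned every 3 months. The effect on the rPFS curve depends on his progression risk after the switch and on how late the sparser scans would have found progression. It could go either way.
- *Switch after new bone lesions appear but before they are confirmed.* Section 8.1.2 (Table 7) requires confirmation at least 6 weeks later. Until then, Table 15 in Appendix G leaves the visit as non-progression. A Section 8.2.8.2 scan 3 months (about 13 weeks) after the last assessment would satisfy the 6-week minimum. A confirmed progression would be dated back to the scan that first showed the second new lesion. Without that scan the event is lost, which raises rPFS for those patients.

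**Step 4. Ask whether a size can be given.** It would need four inputs: the share of patients switching before progression, their risk afterwards, the share of unconfirmed bone findings that would have been confirmed, and the share of sites reading Table 6 literally. The protocol gives none of them.

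The one related figure is the median PFS of 14.9 weeks in the combination cohort of the earlier study (Section 2.3), and it does not supply a sound base:

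- Read as an observed exponential median, it gives 6-month rPFS of exp(−ln 2 × 26/14.9) = 29.8%.
- Treated as an underlying time, with scans at Weeks 6, 14 and 22 laid on top, it gives exp(−ln 2 × 22/14.9) = 35.9%.
- The second reading contradicts its own input. The proportion still progression-free after the Week 14 scan is exp(−ln 2 × 14/14.9) = 52.1%, so the observed median would be Week 22, not 14.9 weeks.

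The base alone moves by about 6 points (35.9 − 29.8 = 6.1) before any assumption about switching. No point shift is reported here.

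**The case against.** The strongest reply is that the operative text already settles the matter. Section 6.6 concerns treatment given alongside AZD4635 and is not a follow-up rule. Section 7.1 separates discontinuation from withdrawal in emphatic terms, and Section 7.1.1 says participation is unaffected. Section 8.2.8.2 lists what ends imaging, and withdrawal by the investigator is not on the list. Section 7.3 lets a patient who withdraws leave treatment and still agree to follow-up. Section 7.1 also names confirmed progression as the reason for stopping ("Confirmed disease progression unless, in the opinion of the Investigator, the patient is still receiving clinical benefit"), which discourages a switch between first sight of lesions and confirmation. Lost scans therefore require a site to put one table cell above several sections.

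Most of this stands. It shows that the intended meaning is probably discontinuation of study treatment, and it keeps the point minor. It does not remove the contradiction. Table 6 is mandatory and does not refer to those sections, and the follow-up option in Section 7.3 is the patient's own consent choice.

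The reply also limits the consequence. Deaths still count for rPFS unless they follow two or more missed radiologic visits, and Section 8.2.8.3 seeks vital status for withdrawn patients. So the literal reading would not erase every event, and OS is less exposed than rPFS.

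A reader might also infer that Section 8.4.5 needs the same correction, because it withdraws a patient with unresolved toxicity from the study where Table 9 only discontinues AZD4635. The documents do not support making that change. The patient there is still to be observed, and the reworded rule could leave someone with unresolved toxicity on the partner antibody. The module appendices that would settle this are not available.

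**Conclusion.** The inconsistency is real, and Table 6 is wrong as written. It is a minor internal contradiction and not a questionable design choice, because the sections that govern discontinuation, follow-up and the endpoints agree with one another.

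The consequence is conditional. If a site applies Table 6 literally to a patient who switches before documented or confirmed progression, rPFS and duration of response are censored contrary to the rPFS definition. Both endpoints are secondary and, under Section 9.2, descriptive. The point makes no claim about the primary endpoints (ORR and PSA50), the sample size or any stated interval.

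A reader might infer that 6-month rPFS would be inflated by some number of points. The documents do not support that. The bone-lesion route pushes upward for the patients it touches, the other route can go either way, and neither frequency is known. Nor do the documents show that any site has read Table 6 this way.

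**What to change.** In the Table 6 row on other investigational and anticancer agents, replace *withdrawn from the study* with *discontinued from study treatment; tumour and survival follow-up continue per Sections 7.1.1 and 8.2.8*.

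The cost is one phrase at the next amendment, with a short note to sites if patients are still on treatment before the primary data cut-off. The bar on concurrent anticancer therapy is unchanged, and the visits and scans are already in Section 8.2.8. Section 8.4.5 should be left as it is.

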 - Anticancer therapy: ≥ 21 days or 5 half-lives (whichever is shorter) of the first dose of study drug. At least 7 days must have elapsed between the last dose of such agent and the first dose of study drug. **Exception:** Androgen-deprivation therapy is required to maintain castrate levels of testosterone (< 50 ng/dL).
 - Concurrent use of hormones for non-cancer-related conditions (e.g., insulin for diabetes and hormone replacement therapy) is acceptable.
 - 13 Major surgery (as defined by the Medical Monitor, excluding placement of vascular access) within 4 weeks of the first dose of study treatment.
 - 14 Minor surgical procedures (as defined by the Medical Monitor) within 7 days of the first dose of study treatment
 - 15 Patient is receiving medications or other products known to be sensitive breast cancer resistance protein (BCRP) or organic anion transporter polypeptide 1 (OATP1B1), OATP1B3, OAT1, organic cation transporter 1 (OCT1), OCT2, multidrug and toxin extrusion protein 1 (MATE1) and P-glycoprotein (P-gp) substrates or potent or moderate inhibitors/inducers of CYP1A2, which cannot be discontinued 2 weeks prior to Day 1 of dosing and withheld throughout the study until 2 weeks after the last dose of AZD4635. See [Appendix J](#) for the list of BCRP, OATP1B1, OATP1B3, OAT1, OCT1, OCT2, MATE1 and P-gp substrates, and CYP1A2 inhibitors and inducers.
 - 16 Concomitant medications with another A₁R antagonist that would increase risk of seizure (e.g., theophylline, aminophylline).
 - 17 Nitrosourea or mitomycin C within 6 weeks of the first dose of study treatment.
 - 18 Ongoing treatment with Coumadin.
 - 19 Receipt of live attenuated vaccine within 30 days prior to the first dose of study drug.
 - 20 Herbal preparations/medications are not allowed throughout the study. These herbal medications include, but are not limited to: St. John's wort, kava, ephedra (ma huang), ginkgo biloba, dehydroepiandrosterone, yohimbe, saw palmetto, and ginseng. Patients should stop using these herbal medications 7 days prior to the first dose of AZD4635. Exceptions may be agreed upon, but the circumstances must be reviewed by the Medical Monitor in advance.
 - 21 Radiotherapy with a wide field of radiation within 4 weeks or radiotherapy with a limited field of radiation for palliation within 2 weeks, of the first dose of study treatment.

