Appendix J Disallowed medications

Contribution of CYP1A2 to AZD4635 metabolism appears to be >80%. The following CYP1A2 strong and moderate inducers and inhibitors (Table 19) are not permitted from 2 weeks prior to the first dose of AZD4635 until at least 2 weeks after the last dose of AZD4635.

Table 19 Examples of CYP1A2 inhibitors and inducers of

CYP1A2	Strong inhibitors	Moderate inhibitors
	Ciprofloxacin, clinafloxacin, enoxacin, fluvoxamine ^(a) , oltipraz, zafirlukast, rofecoxib, Angelica root - Bai Zhi (Angelica dahurica radix)	Methoxsalen, mexiletine ,oral contraceptives,3,4-methylenedioxymethamphetamine (MDMA), etintidine, genistein, idrocilamide, osilodrostat, phenylpropranolamine, pipemidic acid, propafenone, propranolol, troleandomycin, vemurafenib, grepafloxacin, piperine, zileuton
	Strong Inducers	Moderate Inducers
		Phenytoin, rifampin, ritonavir, smoking, teriflunomide

^a Strong inhibitor of CYP1A2 and CYP2C19, and moderate inhibitor of CYP2D6 and CYP3A.

Use of inhibitors or inducers of BCRP and sensitive substrates of OATP1B1/3, OAT1, OCT1, OCT2, MATE1 and P-gp is not permitted from 2 weeks before the first dose of AZD4635 until at least 2 weeks after the last dose of AZD4635.

Examples of sensitive substrates of these substrates above are presented in Table 20.

Information on any treatment in the 4 weeks prior to starting study treatment and all concomitant treatments given during the study with reasons for the treatment should be recorded. If medically feasible, patients taking regular medication, with the exception of examples of known substrates of transporters listed in Table 20, should be maintained on it throughout the study period.

Table 20 Examples of substrates of transporters

Substrate category	Examples of drugs in the category
Sensitive substrates of:	
BCRP	Methotrexate, mitoxantrone, imatinib, lapatinib, sulfasalazine, topotecan, daunorubicin, doxorubicin, SN-38, irinotecan, prazosin, pantoprazole, atorvastatin, fluvastatin, rosuvastatin, simvastatin.

Substrate category	Examples of drugs in the category
OAT1	Adefovir, captopril, furosemide, lamivudine, methotrexate, oseltamivir, tenofovir, zalcitabine, zidovudine, ciprofloxacin, cephaloridine, methotrexate, pravastatin
OATP1B1, OATP1B3	Asunaprevir, atorvastatin, bosentan, danoprevir, docetaxel, fexofenadine, glyburide, nateglinide, paclitaxel, pitavastatin, pravastatin, repaglinide, rosuvastatin, simvastatin acid
OCT1	Metformin, oxaliplatin, aciclovir, ganciclovir

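### The on-study prohibition in Table 6 and Appendix J names BCRP inhibitors and inducers, while the stated risk, exclusion 15 and Table 20 concern BCRP substrates; the CYP1A2 wording also differs, to a lesser degree

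*Protocol*

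**What the plan says.** Four places in the Protocol set the rules for BCRP.

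- **Section 6.6, Table 6, left cell.** AZD4635 is described as an in vitro inhibitor of BCRP and OAT1, so that "there is a risk of DDIs with sensitive substrates of BCRP", and likewise of OAT1. The cell reports modelling that predicts a more than 2-fold rise in exposure to simvastatin, rosuvastatin and atorvastatin. It adds that substrates of OATP1B1/3, OCT1, OCT2, MATE1 and P-gp are also prohibited.
- **Section 6.6, Table 6, right cell.** The conclusion, introduced by *therefore*, prohibits the following: "Use of potent inhibitors or inducers of BCRP and sensitive substrates of OATP1B1/3", with the list of substrates running on to the other transporters, OAT1 among them.
- **Appendix J, text.** "Use of inhibitors or inducers of BCRP and sensitive substrates of OATP1B1/3" and the further transporters is not permitted, from 2 weeks before the first dose until at least 2 weeks after the last.
- **Section 5.2, exclusion 15.** It begins "Patient is receiving medications or other products known to be sensitive breast cancer resistance protein (BCRP" and continues through the other transporters to the word *substrates*. It does not mention BCRP inhibitors or inducers.

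Table 20 in Appendix J gives examples of sensitive BCRP substrates.

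For CYP1A2, Table 5 (restricted medications) says: "Potent inhibitors or inducers of CYP1A2 should be avoided during administration of AZD4635". It then refers to Appendix J for the list. Appendix J opens its rule with "The following CYP1A2 strong and moderate inducers and inhibitors" and says these are not permitted. Exclusion 15 covers potent or moderate agents.

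**The concern.** In Table 6 the rule does not follow from its own reason. The reason concerns drugs whose exposure AZD4635 may raise, that is, BCRP substrates. The rule, joined to it by *therefore*, restricts a different class: drugs that act on BCRP. For OAT1, named in the same reason, the rule does carry over to substrates; for BCRP it does not. Sites are left with a prohibition for which no list is visible, and a list that no prohibiting sentence names.

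This matters mainly for drugs first started on study. Exclusion 15 addresses what a patient is receiving at entry and requires that to be withheld throughout. It does not clearly reach a new prescription. Section 6.6.3 leaves medication not described in Section 6.6 to the Investigator's discretion.

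There is also a smaller point for the data. Section 9.3 removes AZD4635 PK data affected by important protocol deviations from the summaries, and steady-state trough is a secondary endpoint. Whether a moderate CYP1A2 agent counts as a departure from the rules should not depend on whether one reads Table 5 or Appendix J.

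**Working it through.** The plan states no figure to reproduce, so the check is a comparison of current text and a hand count.

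**Step 1. The rules side by side.**

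| Place | Applies to | BCRP | CYP1A2 |
|---|---|---|---|
| Exclusion 15 | Drugs in use at entry, then withheld through the study | Sensitive substrates | Potent or moderate inhibitors/inducers |
| Table 5 | While on AZD4635 | Not addressed | Potent only, to be avoided; refers to Appendix J |
| Table 6, left cell | On study | Risk stated for sensitive substrates; no explicit ban on them | Not addressed |
| Table 6, right cell | On study | Potent inhibitors or inducers | Not addressed |
| Appendix J, text | 2 weeks before first dose to at least 2 weeks after last | Inhibitors or inducers, any strength | Strong and moderate, not permitted |
| Table 20 | Examples | Sensitive substrates | Not addressed |

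For BCRP, two places name inhibitors or inducers and differ on strength. Three concern substrates. For CYP1A2, exclusion 15 and Appendix J agree on strength, and Table 5's sentence is narrower.

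**Step 2. How many listed drugs fall in the gap.**

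Table 20 lists 16 BCRP substrates. Start from these and remove those barred by other wording in Table 6.

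- Also listed in another visible row whose substrates Table 6 prohibits: methotrexate (OAT1); atorvastatin, rosuvastatin and simvastatin (OATP1B1/1B3, the last as simvastatin acid). 16 − 4 = 12.
- Anticancer agents, barred by the first row of Table 6: mitoxantrone, imatinib, lapatinib, topotecan, daunorubicin, doxorubicin, SN-38, irinotecan. 12 − 8 = 4.
- Remaining: sulfasalazine, prazosin, pantoprazole, fluvastatin.

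The anticancer classification is ours; the Protocol does not label these drugs. Any drug wrongly placed in that group would add one to the four. In the other direction, the OCT2, MATE1 and P-gp rows of Table 20 are not visible in the copy reviewed. If they list any of the four, the count falls, possibly to 0. Among listed examples, four is therefore an upper bound given the classification. Table 20 gives examples only, so unlisted BCRP substrates are not counted.

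**The case against.** The strongest reply is that a careful site would infer a substrate ban. The left column of Table 6 is the one headed as prohibited medication, and its *also* presupposes that BCRP and OAT1 substrates are already barred. Table 6 points to Appendix J, which is titled as disallowed medications and whose only visible BCRP list is of substrates. Appendix J exempts Table 20 drugs from its instruction to keep patients on regular medication. Section 6.6 opens by bringing Appendix J drugs under its rules for the whole treatment period. All of this stands, and it makes the intention readable. It does not put the ban into words: the right cell and the Appendix J sentence state another class. The opening of Section 6.6 offers prohibition or caution without saying which applies.

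A reader might infer that a site following Table 6 could start the three statins for which the modelling predicts more than 2-fold exposure. The documents do not support that. All three come under the OATP1B1/3 substrate ban through Table 20, simvastatin in its acid form. The modelling figure describes the risk that the sponsor identified and does not measure the gap.

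On CYP1A2, a reader might infer that Table 5 permits moderate agents. It does not say so. Its row label carries no strength limit, and it refers to Appendix J for the prohibited list, which covers strong and moderate agents and matches exclusion 15. What remains is narrower and softer wording in Table 5.

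**Conclusion.** The contradiction is real, stands in current text and concerns an operative safety rule. The two sentences that prohibit on-study use name BCRP inhibitors or inducers, while the stated risk, the entry criterion and the drug list concern BCRP substrates. Table 6 and Appendix J also disagree on whether only potent agents are meant.

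Its reach is limited. Among the listed examples, at most about four drugs could be newly started without breaching Table 6's wording, given the classification of the eight anticancer agents and the missing rows of Table 20. The number of patients affected cannot be derived from the Protocol. It does not show that adverse events would be misattributed to the combination. Nothing here touches the sample size or the primary endpoints.

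The CYP1A2 difference is secondary. This should be corrected as a drafting inconsistency in a safety rule. The review takes no position on which class or strength should be restricted.

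**What to change.** Reconcile exclusion 15 in Section 5.2, Tables 5 and 6 in Section 6.6, and the text and Table 20 of Appendix J, so that for both BCRP and CYP1A2 they agree on:

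- class: substrate, or inhibitor/inducer;
- strength: potent only, or potent and moderate;
- status: to be avoided, or not permitted;
- timing: the same rule at entry and for drugs newly started on study.

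Each prohibited class should match the list it refers to. The opening of Section 6.6 should say which Appendix J drugs are prohibited and which are to be used with caution. The sponsor decides which wording stands.

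The cost is a wording change to the Protocol and a notification to sites. No new data, analyses or procedures are needed.
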